In the case of isolated deviations from the protocol, these are registered in the data collection form, which is provided with a space to record any variation or comment the doctor deems appropriate. In case, during the study, a modification to the protocol is deemed necessary, the investigator communicates this need to the sponsor, who convenes the investigator of the coordinator centre, the study coordinator and any other experts in the field, and discusses the proposed variations and, where appropriate, submits a request for amendment to the Ethics Committees to approve the changes deemed necessary.

Adverse Events

Despite all the information in our possession and physical characteristics and performances of the device that do not suggest the possible occurrence of and adverse event, this section of the Protocol takes into consideration the possibility that said event could take place.

An Adverse Event (AE) is any untoward change in the state of health, or side effect, or unexpected benefit that could occur in a patient involved in in a clinical study while they receive the treatment or within a given timeframe following the conclusion of the therapy, not necessarily related to said treatment or clinical experimentation. An AE can consist in any unfavourable and/or unexpected sign or symptoms (including abnormal results from laboratory testing) or a pathology temporarily associated with the use of a medicinal product (subject of the experimentation) or experimental device, that whether or not is related to that medicinal product or device.

The morbid condition of each patient will be monitored the whole time of the study. During each visit any sign manifested by the patient will be carefully observed, in fact, the subject will be encouraged to report any symptom with direct questions, such as: "How have you been feeling since our last visit?". They will also be prompted to spontaneously report any adverse events that occurred during the study.

Any significant clinical anomaly encountered over the course of the study will be monitored and observed until its normalisation, or until it will be clinically explainable.

Serious Adverse Events

L.U.C.E. Study Protocol version 3.0 (24/02/2020)

A Serious Adverse Event (SAE) is defined as any unfavourable medical occurrence that, at any dosage, will result in any of these consequences:

- Death of the patient
- Any inauspicious outcome in the short term

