All the Adverse Events must be registered using the accepted diagnosis, whenever possible. Any alteration of laboratory results, vital sign, or reported by the physical examination must not be registered as an Adverse Event if it is known that they constitute a symptom or a sign of a diagnosis already reported as it is. For example: an ST segment elevation detected by an EKG and an increase of creatine phosphokinase are both well known signs of myocardial infarction and it will not be necessary to report them if myocardial infarction is already registered ad an Adverse Event. However, if both of them happen separately and a myocardial infarction has not been diagnosed, this eventuality must be registered as an Adverse Event.

Severity Classes and causal relationship of Adverse Events must be defined using the following parameters:

Gravity:

- *Mild* easily tolerated, does not interfere with daily activities
- *Moderate* causes some interference with daily activities
- Severe all daily activities are completely compromised

Relationship with procedures required by the study:

- *Not correlated* temporal association among the Adverse Event and the use of the product results in an extremely unlikely association between the two.
- *Possibly correlated* the adverse event occurs with a timing compatible with the beginning of the use of the product employed in the study, but it is also attributable to the clinical condition of the patient or the procedures/condition of the study.
- Undoubtedly corelated the adverse event occurs with a timing compatible with the beginning of use of the product employed in the study, recedes with its discontinuation and re-emerges when its reintroduced.

In addition to registration in the Data Collection Form (AE), the Adverse Events considered serious (SAE) that comprehend Suspicious and Unexpected Adverse Reactions (SUSAR) must be reported by the ricercatore in the Serious Adverse Events Report Form. This last document must be compiled and sent immediately to the Clinical Research Coordinator of the study, namely withing twenty-four from the moment the research staff diagnosed an SAE.

Safety follow-up for subjects withdrawn from the study

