The subjects that withdrew from the experimentation after the treatment with the device under study for any reason, will undergo a continued monitoring of the Adverse Events in place until the results from the tests related to the Adverse Event, and required by the SOC, will recover to baseline or until the investigator will determine that those events are not clinically relevant anymore. The subjects who present Adverse Events up until thirty days from the last visit or the last follow-up check (whichever of the two eventualities is the latter) will be monitored until their test results are not recovered to baseline, or until the investigator does not determine that the results are not clinically relevant.

Safety follow-up for subjects who have completed the study

All the subject who still present Adverse Events upon completion of the study will be monitored until the test results are not back to baseline, or is no longer expected from them to change, or until the investigator does not determine that those results are no longer clinically relevant.

Amendments to the clinical evaluation plan

If, during the study, a modification to the protocol is deemed necessary the investigator communicates this need to the sponsor, who convenes the investigator of the coordinator centre, the study director and any other experts in the field, and discusses the proposed variations and, where appropriate, submits a request for amendment to the Ethics Committees to approve the changes deemed necessary.

If a substantive amendment request is necessary, the clinical trial will be suspended until approval has been received by the relevant ethics committees.

Early termination and suspension of clinical evaluation

In the event of suspension or early termination of the study by the sponsor, taken as a safety measure due to events related to the conduct of the study that may affect the health of the patients recruited, the promoter is required to notify the Ministry of Health and the Ethics Committees involved within 90 days from the recruitment of the last patient or the early closure. In case of suspension or early termination of the study not for safety reasons, the sponsor shall justify and explain their decision. The suspended clinical trial cannot be reactivated unless a substantive amendment and the positive opinion of the Ministry of Health and the Ethics Committees have been submitted.

Statistics

Calculation of the sample size

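### Stray negations reverse four of the five conditions for ending adverse-event monitoring in the 30-day and completer follow-up rules (minor wording error)

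*Combined protocol and SAP*

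**What the plan says.** Four sentences of the protocol govern how long an adverse event or clinical anomaly is followed.

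- **Adverse Events** (general rule, limited to anomalies that are significant): the text is that a "clinical anomaly encountered over the course of the study will be monitored and observed until its normalisation, or until it will be clinically explainable".
- **Safety follow-up for subjects withdrawn from the study, first sentence** (events in place at withdrawal): monitoring runs until test results "will recover to baseline or until the investigator will determine that those events are not clinically relevant anymore".
- **Same section, second sentence** (events up to thirty days after the last visit or follow-up check, whichever is later): monitoring runs "until their test results are not recovered to baseline, or until the investigator does not determine that the results are not clinically relevant".
- For completers, **Safety follow-up for subjects who have completed the study** gives this scope: "All the subject who still present Adverse Events upon completion of the study will be monitored". The first two limbs of its rule are that these people "will be monitored until the test results are not back to baseline, or is no longer expected from them to change". The third limb, which turns on the investigator's judgement, reads "until the investigator does not determine that those results are no longer clinically relevant".

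**The concern.** The first two sentences end follow-up once the problem has resolved, been explained or been judged irrelevant. The last two attach the end of follow-up to the opposite events: results that have *not* recovered, and an investigator who has *not* made a determination. The limbs are joined by *or*, so meeting one is enough.

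These are operative safety rules. The completer sentence exists for people who still have an adverse event at study end, and its literal text releases those people. Safety of treatment is the first-listed secondary endpoint, and the Monitoring plan section has conduct checked against the protocol. A rule that runs backwards is a poor standard for that check.

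**Working it through.** No figure in the plan is at issue, so the check is a count of conditions followed by their logic.

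**1. Count of end conditions**

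| Sentence | End conditions | Reversed |
|---|---|---|
| Withdrawn subjects, events in place | 2 | 0 |
| 30-day sentence | 2 | 2 |
| Completer sentence | 3 | 2 |

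In the 30-day sentence both limbs are reversed: it starts "will be monitored until their test results are not recovered to baseline", and the investigator limb is negated too. The second *not* in that limb, the one attached to clinical relevance, is intended; the stray one is in *does not determine*.

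In the completer sentence the baseline limb and the investigator limb are reversed. The middle limb, on results no longer expected to change, has the right direction.

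Reversed in the two affected sentences: 2 + 2 = 4, out of 2 + 3 = 5 conditions.

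**2. What the literal rule does**

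Let R = results at baseline, D = investigator has determined that the results are not clinically relevant, E = results no longer expected to change (1 = true, 0 = false).

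*30-day sentence.* The intended rule stops if R or D. The literal rule stops if not-R or not-D.

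| R | D | Intended | Literal |
|---|---|---|---|
| 0 | 0 | monitor | **stop** |
| 0 | 1 | stop | stop |
| 1 | 0 | stop | stop |
| 1 | 1 | stop | **monitor** |

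The intended rule monitors in one of four states (unresolved and undetermined). The literal rule also monitors in one of four, but in the opposite one (resolved and judged irrelevant). The rules differ in 2 of 4 states.

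*Completer sentence.* The intended rule stops if R or E or D. The literal rule stops if not-R or E or not-D.

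- With E = 1 (four states), both rules stop.
- With E = 0 (four states), the table above applies again. The intended rule monitors only at R = 0, D = 0; the literal rule monitors only at R = 1, D = 1.

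Each rule therefore monitors in 1 of 8 states, and they differ in 2 of 8.

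In both sentences the literal rule stops in the one state where the intended rule continues. These counts describe the logic of the sentences. The states are not equally likely, so the counts are not a measure of risk.

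**3. Whether other text corrects it**

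The first sentence on withdrawn subjects covers only withdrawn subjects with events in place; applying it to completers is by analogy. The general rule under Adverse Events covers significant anomalies met during the study and has a different second limb (clinically explainable). Neither is stated to override the two faulty sentences.

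**The case against.** The strongest reply is that this is a translation slip that nobody would act on. An Italian word is left in the English text ("must be reported by the ricercatore in the Serious Adverse Events Report Form"), and all four stray negations sit in clauses introduced by *until*, while the one limb without its own *until* is correct. That pattern fits a literal rendering of an Italian construction. Sites may have worked from an Italian text without the error; the documents do not say which language version governs. A rule that releases everyone it names defeats itself, so an investigator would read it sensibly. The general rule under Adverse Events also reaches a completer whose significant anomaly began during the study.

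Most of this stands, and it is why the point is minor. It does not remove the error. A translation slip is the probable cause, but it cannot be confirmed from the documents, and the first sentence on withdrawn subjects puts the same kind of condition correctly. The general rule is limited to significant anomalies during the study. No text states the completer rule correctly, so the reader has to infer it. The sentences are complete and the pattern occurs four times under two headings, so a PDF reading fault or redaction is not a plausible explanation.

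**Conclusion.** The point holds: the text is wrong as written, and the severity is minor. Four of five end conditions are reversed: both in the 30-day sentence and two of three in the completer sentence. Followed literally, the text would end monitoring for subjects with unresolved results and no investigator judgement.

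This rests on reading *or* as making each limb sufficient, and on taking the intended direction from the correctly worded sentences. That intent is clear enough for the practical effect to be small. How many subjects could be affected is not estimated.

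**What to change.** Remove only the four stray negations:

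- **30-day sentence:** *are not recovered* becomes *are recovered*; *does not determine* becomes *determines*. The *not* attached to clinical relevance stays.
- **Completer sentence:** *are not back* becomes *are back*; *does not determine* becomes *determines*. The phrase on results no longer being clinically relevant stays. The middle limb becomes *are no longer expected to change*, which mends the grammar without altering the meaning.

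If an Italian text is in use at the sites, check the same two sentences there.

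The cost is four word-level edits and one grammar tidy, with no new visits, tests or data. The protocol sends changes through the sponsor and, where appropriate, the Ethics Committees, and it suspends the trial while a substantive amendment is pending. The correction is therefore best carried in the next protocol version.

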- Pregnancy or breast feeding;
- Patients with neoplasms or other diseases involving the use of cytostatic or immunosuppressive drugs;
- Patients with limited lifespan;
- Patients with photosensitizing illnesses or that take photosensitizing drugs.

All inclusion and exclusion criteria must be satisfied before recruitment. Any concomitant pharmacological therapy must be maintained.

Number of patients expected to enroll

A total of 80 subjects will be recruited, 40 per arm at the facilities involved in the clinical study. Each one of the four sites involved will enroll 20 patients. The expected time for enrollment is 7 months. Since this is a multicentric investigation with competitive recruitment the number of patients per site can vary, depending on the recruitment capability of each site.

Enrollment point

Once the patient has signed the informed consent, the Principal Investigator enters the data in the Enrollment Registry, carefully checking all the inclusion and exclusion criteria; if all criteria are met, the patient is considered to be enrolled in the clinical study.

Number of experimental devices expected to be used

Each experimental site will be equipped with an EmoLED medical device. In the study a total of 4 EmoLED medical devices will be made available.

Time-frame of the study

The study lasts 12 moths, with a recruitment time of 7 months.

Medical and surgical procedures

The lesions will be cleansed with saline solution and, if necessary, surgical debridement will be performed with the most suitable method. At this point, if patient is included in Group 2, the EmoLED treatment starts. After EmoLED application (Group 2) or after cleansing (Group 1), a polyurethane foam dressing will be applied on the lesion. In case of clinical signs of infection, a silver dressing will be applied.

Then an elasto-compressive double layer dressing of the limb with cohesive fixation bielastic latex-free bandage will be carried out.

The treatment with EmoLED, in addition to the SOC, will be performed during each visit for 60 seconds on each 5 cm diameter sub-area of the selected lesion.

In case of multiple lesions matching with both inclusion and exclusion criteria, they will be all treated following the same protocol, depending on the group to which the patient belongs; in this case the Principal Investigator will fill out a data-collection form and take pictures just of the lesion with the wider area.

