Known or predictable factors that may impair outcomes and interpretation of outcomes

A different therapy standard between participating centers and/or within the same center can lead to very variable outcomes between one patient and another, all other conditions being equal. This problem is tackled by indicating in detail the therapy to be followed depending on the type of lesion.

An incorrect recording of photographic images does not make it possible to determine the area of the lesion via software. This problem is tackled by providing precise instructions on the correct use of the tools available for the retrieval of images.

Discontinuity of patients can affect recovery times. Before recruiting a patient, the doctor ensures that the patient is available to go, with the required timing, to the clinic, for the scheduled visits. This fact is underlined several times when providing study information to the patient.

Interruption and withdrawal of subjects from the clinical trial

Patients who miss the visits for two consecutive weeks, before/until the 14th week, and the patients who miss the visits for one week, after the 14th week, will be reached by phone by the Principal Investigator to assess their availability to go on with the study; in the event that the patient does not intend to continue with the visits at the centre, they will be excluded from the study. Also, the patient who will turn out to be absent for more than half of the sessions will be excluded as well.

Following the resignation or withdrawal from the study by a patient, their data collection form will be identified, scanned and archived.

If a patient withdraws from the study, the Principal Investigator or his delegate records the event in the Patient Identification Register and on the Data Collection Form and stores all documentation.

Monitoring plan of the clinical investigation

To guarantee the conformity with ICH/GCP guidelines, the Clinical Research Coordinator (CRC) will be responsible for the study to be carried out in full observance of the Standard Operating Procedures, of the Protocol and other written instructions.

The main responsibilities of the CRC are to ensure adherence to the Protocol, to make sure that the data are accurately and fully registered and reported and to verify that the Informed Consent was obtained and registered for each subject before the beginning of the study.

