80 patients will be recruited during the study; they will be randomized 1:1 to the standard treatment group and the EmoLED Protocol group. In the control group, which follows the standard treatment, patients will be visited twice a week. The EmoLED experimental Protocol group will undergo medical examination once a week; in this case, therapy will consist in the standard treatment plus EmoLED treatment.

This sample size is sufficient to compare the average rate of the injured area reduction, considering Student-T test for the comparison between independent samples, by establishing $\alpha = 0.05$, power level (1- β) = 0,8, under the assumption to have an area reduction rate after 16 weeks amounting to 50% in Group 1 (control group), a difference of 20% between Group 2 (experimental group) and Group 1, a standard deviation of averages equal to 50% of the mean values and a bilateral hypothesis.

Statistical analysis

The average rate of reduction of the injured area between the two groups will be compared using the Student-T-test, the quality of life in both groups at the baseline, after 16 weeks and the difference with the baseline will be compared using Student-T-test for independent samples.

Linear regression models will be used to value the differences between the groups to exclude any confounding factors. Due to the usually asymmetrical nature of cost distribution, the comparison of the costs related to the treatment and control group, in both the NHS and society perspective, will be made using the non-parametric Mann-Whitney U test.

Generalized linear regression models will be used to value the differences between the groups to eliminate any confounding factors.

The cost-effectiveness of both treatments in the time frame of the study (16 weeks) will be valued by calculating the incremental cost-effectiveness ratio (ICER) and expressed in terms of incremental costs for "quality adjusted years (QALY).

Extrapolations of results about the cost-effectiveness that simulate longer time-frames will be made considering decision-making models (e.g. Markov models) and eventually including the data gathered during the study with literary data and/or evidence from other studies.

Data publication policy

L.U.C.E. Study Protocol version 3.0 (24/02/2020)

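### Patients are excluded after randomization, partly on attendance, with no rule keeping them in the primary analysis and no allowance for their loss in the sample size

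*Combined protocol and SAP*

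**What the plan says.** Under Statistics, the calculation of the sample size opens with "80 patients will be recruited during the study" and adds that "they will be randomized 1:1 to the standard treatment group and the EmoLED Protocol group". The section on the number of patients repeats the figure: "A total of 80 subjects will be recruited, 40 per arm at the facilities involved in the clinical study". The claim made for this number is "This sample size is sufficient to compare the average rate of the injured area reduction". The calculation is made "considering Student-T test for the comparison between independent samples", with α = 0.05, power 0.8 and "a bilateral hypothesis". It assumes a 50% area reduction in the control group at 16 weeks, a 20% difference between groups, and a standard deviation equal to half of the mean values. No expected loss is given.

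The section on interruption and withdrawal removes patients after allocation in two ways. Patients who miss visits are telephoned, and those who do not intend to go on are excluded. Then: "Also, the patient who will turn out to be absent for more than half of the sessions will be excluded as well". The withdrawn patient's form is scanned and archived. The section on measurable parameters plans 32 visits in Group 1 and 16 in Group 2.

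The primary endpoint is compared at week 16. A picture is taken at every visit, but the section on image acquisition has lesion area measured only at the start, middle and end of treatment. The plan defines no analysis population, no method for a missing week-16 area and no replacement of lost patients.

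**The concern.** Two things meet here. First, the power is stated for patients recruited, whereas the t-test uses patients with an outcome, and the plan's own rules can make the second number smaller than the first.

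Second, and more important, the exclusions depend on what happens after randomization. Attendance may be related to how the ulcer is doing and to how demanding the schedule is, and the schedule differs by design. The same fraction, one half, is applied to 32 sessions in one arm and 16 in the other. A control patient who comes once a week for 15 weeks and no more has missed 32 − 15 = 17 sessions and meets the exclusion rule. An EmoLED patient with the same 15 visits has missed 16 − 15 = 1. If such exclusions carry through to the analysis, the two groups are no longer the groups that were randomized. A larger sample would not cure that.

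**Working it through.** **Inputs.** From the sample-size paragraph: control mean 50, difference 20 (read as percentage points, so EmoLED mean 70), SD half of each mean (25 and 35), two-sided α 0.05, power 0.80, t-test for independent samples. Recruited: 40 per arm. Loss rates are assumptions, because the plan states none.

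**Reproducing the plan's figure.**

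- Pooled SD = √((25² + 35²)/2) = √925 = 30.41.
- Normal approximation: n per arm = (1.960 + 0.842)² × (25² + 35²)/20² = 36.3, so 37.
- Exact t-test (noncentral t): 37.29, so 38 per arm, 76 in all.
- Power at 40 per arm: standard error = √(25²/40 + 35²/40) = 6.80; noncentrality = 20/6.80 = 2.94; 78 degrees of freedom; critical value 1.991; power 82.8%.

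So 80 analysed patients are sufficient, as the plan says. Reading the 20% as relative (50 against 60) would need about 121 per arm and does not reproduce 80, so the percentage-point reading is used.

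**A second reading of the SD.** The wording also allows one common SD of 30, half of the average mean of 60. The t-test then needs 37 per arm, and power at 40 per arm is 83.8%.

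**Power when 80 are recruited and some yield no outcome** (t-test, equal loss in both arms):

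| Assumed loss | Analysed per arm | SD 25 and 35 | Common SD 30 |
|---|---|---|---|
| 0% | 40 | 82.8% | 83.8% |
| 5% | 38 | 80.8% | 81.8% |
| 7.5% | 37 | 79.7% | 80.8% |
| 10% | 36 | 78.6% | 79.7% |
| 15% | 34 | 76.2% | 77.3% |
| 20% | 32 | 73.6% | 74.7% |

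With SDs of 25 and 35, 75 analysed patients (37 and 38) still give about 80%. The normal approximation is slightly more generous: 37 per arm suffices with SDs of 25 and 35 (80.7%), and 36 with a common SD of 30 (80.7%). Across these readings the margin is two to four patients per arm, that is 5% to 10%.

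**Routes to a missing outcome.** The plan names four: not continuing after missed visits; absence from more than half of the sessions; a picture from which the area cannot be determined; and destruction of data when consent to data processing is withdrawn. The second is the only one set by an attendance threshold alone. It means more than 16 missed visits of 32 in control and more than 8 of 16 with EmoLED. Pictures from the visits that such a patient did attend already exist, so their exclusion from the comparison would be a choice of analysis and not a lack of data.

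**The case against.** The strongest reply is that nothing is miscalculated. The stated power is right for 80 analysed patients, and 40 per arm is exactly what 38 becomes after a 5% inflation (38/0.95 = 40). That stands, although the plan does not say that such an allowance was intended.

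A reader might infer that the stated power fails at any loss above 5%, or that at least 76 of 80 patients must be evaluable. The documents do not support either. With SDs of 25 and 35, 75 analysed patients still reach about 80%, and a common SD of 30 tolerates three losses per arm. The shortfall at 10% loss is at most 1.4 points, which is small beside the uncertainty in the assumed means and SD.

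It is also fair that the plan says excluded from the study, not excluded from the analysis, and that it archives the forms. So the loss of outcomes is not certain. But nothing states the opposite, and a patient who leaves early has no week-16 picture and no substitute rule. The ambiguity is itself what needs settling.

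Finally, the plan takes steps against poor attendance: availability is checked before recruitment, and absentees are telephoned. It mentions discontinuity because it can affect recovery times. It should not be read as the plan's forecast of a high loss rate.

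**Conclusion.** The point holds as a gap in the analysis plan, not as an arithmetic error. Randomized patients can be excluded on later behaviour, under a rule applied to schedules of 32 and 16 visits, and no text keeps them in the week-16 comparison. Followed as written, this risks bias. Its direction and size cannot be computed from the documents.

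The effect on power is secondary and modest: 82.8% with no loss, a margin that covers roughly 5% to 10% loss, and about 74% to 77% at 15% to 20% loss. These figures rest on means of 50 and 70, on SDs of either 25 and 35 or a common 30, on equal loss in both arms, on assumed loss rates, and on lost patients contributing no outcome.

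**What to change.** In the statistical analysis section, state that:

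- Exclusion from the study or missed sessions do not remove a patient from the primary analysis. All randomized patients are analysed in their assigned group.
- When the week-16 area is missing, the pictures already taken are used, either by measuring the last available one or by a model on the available areas. Choose one method before the data are seen. Patients whose data had to be destroyed are counted and reported by arm.
- Any set defined by attendance serves only as a sensitivity analysis.

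In the sample-size paragraph, add that 80 randomized patients give about 83% power if all are analysed, about 79% with 10% loss and about 74% with 20% loss (means 50 and 70, SDs 25 and 35, two-sided 0.05), and say that the loss rates are assumptions. State in the same place which SD was used.

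The cost is a few sentences, some extra image measurement and a slightly less favourable power statement. Enrolment, visits and patient management are unchanged.
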